4.0 11 Mar 2025 [name], [name], [name], [name] The protocol is aligned with SAP 1.0 (11 [name], [name], [name], [name] Mar 2025) on the following points: [name], [name], [name], [name], [name], [name] 1) Nearly 18% of all standardised LSOA11 intervention unit were fragmented while this was only true for a few units in the feasibility study. By 'fragmented' we mean that the LSOA11 units were only partly exposed to the intervention. This is particularly the case for smaller schemes that have 'bespoke' (rather than administrative) boundaries. SAP now details how this problem is approached in a set of sensitivity analyses weighing up selection bias against measurement error (Section 18. Analysis Plan). 2) At the data extract stage, University of Liverpool recommended focusing on emergency hospital admissions rather than just hospital admissions for the outcome indicators they produce under licence with NHS. The authors agreed to this change by email in July 2024 as this is in line with the literature on preventable hospitalisation (Section 18. Analysis Plan). 3) University of Glasgow (pers. comm., 17 Jun 2024), the owner of the Zoopla rent data, does not recommend combining data from before and after they changed the way they scrape the data from the Zoopla website, referred to as Generations 1 and 2. Consequently, the time series available for analysis is based on Generation 1 data. The first and last full year of data were 2012 and 2018, respectively. Therefore, 2012-2018, will be studied for this outcome instead of 2011-2019 (Section 18. Analysis Plan). 4) Staggered Difference-in-Differences with Propensity Score Matching is the primary evaluation method. Staggered Synthetic Difference-in-Differences (SDID) will now be carried out too. In case the Parallel Trends assumption is violated for a given outcome, SDID will become the primary method instead. We will restrict the analyses to schemes implemented 2012-2019 as the SDID method requires at least 1 year of pre-intervention data (Section 18. Analysis Plan).

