The recent literature on difference-in-differences has proposed alternative estimators that overcome the problem of the "forbidden" comparison between treated and already-treated units by making transparent exactly which units are being used as comparison [29]. We will apply the Callaway and Sant'Anna estimator as our main method [30]. This estimator allows for arbitrary treatment effect heterogeneity and dynamic effects by deconstructing the estimation of the overall treatment effect into estimation of so-called group-time average treatment effects. We will apply different aggregation schemes to explore the overall effect as well as treatment effect heterogeneity over time and across groups.

To assess the plausibility of the parallel trends assumption, we will examine the trends in the outcome measures for the treatment and control units in the before period by plotting the raw data over calendar time for the treatment and control units, with the treatment units and their matched control units. We will test if the estimated treatment effects for the three years before the intervention are jointly statistically significantly different from zero. Recent reviews discuss the difficulties with formally testing parallel trends as the analysis may be underpowered [29,31]. Analysts are advised to also assess event time plots and to exercise a degree of pragmatism in cases of small deviations from no-effect before the intervention.

If the parallel trends assumption seems implausible, we will use Synthetic Difference-in-Differences (SDID) instead of DiD as the primary method [32,33]. If the parallel trend assumption is plausible, we will use SDID for our primary outcome to assess the sensitivity of our results to the specific method. SDID finds controls matched on the pre-intervention evolution of outcomes through a weighting strategy and thereby ensures parallel trends in the pre-intervention period. Simulations have shown that SDID performs well compared to other commonly used methods [34]. We will use the same set of LSOA-level covariates for the synthetic controls as for the propensity score matching (see Table 4).

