# 11. Sample size

#### *Individual-level outcomes*

For the individual-level outcome measures, we estimate that the APS includes about 1,000 respondents per year who live in private rented accommodation in LSOAs covered by SL schemes, so over our 2012 to 2019 sample period we expect to observe around 8,000 individuals in the intervention group (5.5% of the England population live in the schemes included in the study). The number of APS participants in the matched comparison LSOAs will be approximately 3000 per year if we match 3 control LSOAs to every intervention LSOA.

As the power calculation for our staggered treatment timing difference-in-differences design with repeated cross-section data would be very complicated, we ran a power calculation for the canonical difference-in-difference design with one pre- and one post-intervention observation to get a broad idea of the statistical power of our analysis. The power calculations are based on a bootstrapping algorithm with 1,000 repetitions with 95% significance level and a 3:1 ratio between control to intervention units. The outcome variable was designed as normal-distributed and z-standardised in an artificial dataset. With just 1,000 respondents – the potential annual number of respondents in treated areas – the minimum detectable difference would be 30% of an SD (Table 1).

Table 1 Power calculations based on bootstrapping algorithm with 1,000 repetitions for a DiD design with 95% significance level, one pre- and one post-intervention observation, and 3:1 ratio between control to intervention units (Burlig et al. 2020) [36]. The outcome variable was designed as normal-distributed and z-standardised. Cells shaded in grey indicate power calculations at or above 80%. A unit can correspond to either a respondent or a LSOA area depending on the context. N corresponds to the number of treated units.

| N    | 10%SD | 15%SD | 20%SD | 25%SD | 30%SD |
|------|-------|-------|-------|-------|-------|
| 1000 | 0.167 | 0.291 | 0.523 | 0.694 | 0.837 |
| 1500 | 0.195 | 0.440 | 0.637 | 0.864 | 0.953 |
| 2000 | 0.272 | 0.540 | 0.800 | 0.934 | 0.989 |
| 2500 | 0.333 | 0.659 | 0.884 | 0.972 | 0.997 |
| 3000 | 0.379 | 0.706 | 0.923 | 0.987 | 0.998 |
| 3500 | 0.423 | 0.787 | 0.958 | 0.989 | 1.000 |
| 4000 | 0.515 | 0.833 | 0.979 | 0.997 | 1.000 |
| 4500 | 0.568 | 0.876 | 0.988 | 0.999 | 1.000 |
| 5000 | 0.593 | 0.894 | 0.993 | 0.998 | 1.000 |
| 5500 | 0.652 | 0.930 | 0.993 | 1.000 | 1.000 |

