**Population turnover index**: An increase in population turnover might indicate unintended consequences of SL. The population turnover index is based on a combination of electoral roll and consumer data [45].

**Tenants' rent (£):** We have gained access to Zoopla Property Data through the Urban Big Data Centre at the University of Glasgow [46]. Zoopla is one of the largest online property advertising companies. The Zoopla data affords a much higher level of granularity than government data on property rents, which are only available at regional level. The data are based on daily extractions, so they reflect day-to-day advertising rather than stock value at any given moment.

University of Glasgow (pers. comm., 17 Jun 2024), the owner of the Zoopla rent data, does not recommend combining data from before and after they changed the way they scrape the data from the Zoopla website in 2019. The first full year of data is 2012. Therefore, for this outcome measure we will study only 2012-2018 instead of 2011-2019.

Listings were selected that qualified on the following criteria (Figure S2): Generation 1 Zoopla data, rentals, residential 2-bedroom properties, non-missing last marketed data 2012-2018, England, first listing per property per year.

We will use the mean rent for a 2-bedroom home with the bottom and top centiles removed to address outlier issues. We will also study the same for 2-bedroom flats ('flat' or 'block of flats') as the most commonly occurring property type.

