As the power calculation for our staggered treatment timing difference-in-differences design with repeated cross-section data would be very complicated, we ran a power calculation for the canonical difference-in-difference design with one pre- and one post-intervention observation to get a broad idea of the statistical power of our analysis. The power calculations are based on a bootstrapping algorithm with 1,000 repetitions with 95% significance level and a 3:1 ratio between control to intervention units. The outcome variable was designed as normal-distributed and z-standardised in an artificial dataset. With just 1,000 respondents – the potential annual number of respondents in treated areas – the minimum detectable difference would be 30% of an SD (Table 1).

Table 1 Power calculations based on bootstrapping algorithm with 1,000 repetitions for a DiD design with 95% significance level, one pre- and one post-intervention observation, and 3:1 ratio between control to intervention units (Burlig et al. 2020) [12]. The outcome variable was designed as normal-distributed and z-standardised. Cells shaded in grey indicate power calculations at or above 80%. A unit can correspond to either a respondent or a LSOA area depending on the context. N corresponds to the number of treated units.

Ν	10%SD	15%SD	20%SD	25%SD	30%SD
1000	0.167	0.291	0.523	0.694	0.837
1500	0.195	0.440	0.637	0.864	0.953
2000	0.272	0.540	0.800	0.934	0.989
2500	0.333	0.659	0.884	0.972	0.997
3000	0.379	0.706	0.923	0.987	0.998
3500	0.423	0.787	0.958	0.989	1.000
4000	0.515	0.833	0.979	0.997	1.000
4500	0.568	0.876	0.988	0.999	1.000
5000	0.593	0.894	0.993	0.998	1.000
5500	0.652	0.930	0.993	1.000	1.000
6000	0.685	0.946	1.000	1.000	1.000
6500	0.727	0.962	0.998	1.000	1.000
7000	0.767	0.973	1.000	1.000	1.000
7500	0.755	0.982	1.000	1.000	1.000

p.12

8000	0.797	0.986	1.000	1.000	1.000
8500	0.811	0.992	1.000	1.000	1.000
9000	0.839	0.994	1.000	1.000	1.000
9500	0.850	0.994	1.000	1.000	1.000
10000	0.870	0.999	1.000	1.000	1.000

Area-level outcomes

For the area-level outcomes, our main analysis will examine 1,635 treated LSOAs, which would give a minimum detectable difference of 25% of an SD (Table 1).

12. Sampling procedure

Our intervention group will include all selective licensing schemes in England with start dates between 2012 and 2019, as identified by Freedom of Information (FOI) requests to all English local authorities. Comparison areas will be identified through matching (see Section 18).

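### Rent data cover 2012–2018 but the treated sample still takes every 2012–2019 start, leaving 168 LSOAs with no pre-licensing year and 42 with no post year; the stated APS period needs the same reconciliation

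*Protocol*

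**What the plan says.** **Rent window.** Section 14a (Tenants' rent) of both documents explains that the listings from before and after a 2019 change in scraping should not be combined. It adds "The first full year of data is 2012" and concludes "Therefore, for this outcome measure we will study only 2012-2018 instead of 2011-2019".

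**Treated sample.** SAP section 12: "Our intervention group will include all selective licensing schemes in England with start dates between 2012 and 2019". Section 18 of both documents codes each LSOA by the first year it was treated and fixes that allocation afterwards. Section 9a reports effects over event years 0 to 5, so the start year counts as exposed.

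**Minimum pre-period.** Protocol section 2, version 4.0, point 4: "We will restrict the analyses to schemes implemented 2012-2019 as the SDID method requires at least 1 year of pre-intervention data". The 2011 schemes were removed under this rule.

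**APS.** Protocol section 11 says "we estimate that the APS includes about 1,000 respondents per year who live in private rented accommodation in LSOAs covered by SL schemes", and continues "so over our 2012 to 2019 sample period we expect to observe around 8,000 individuals in the intervention group". SAP section 11 is the same.

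**Pre-trend test.** Section 9a, individual-level outcomes: "We will test if the estimated treatment effects for the three years before the intervention are jointly statistically significantly different from zero". For area-level outcomes, section 9a describes raw-data plots and an event-study regression for each group.

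**Subgroup.** Section 18 names five larger schemes: Newham (2012), Barking and Dagenham (2014), and Croydon, Liverpool and Waltham Forest (2015).

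**The concern.** Admitting 2012 starts under a rule of at least one pre-intervention year works only if outcome data begin in 2011. When the rent window was cut to 2012–2018, the scheme list was not cut with it.

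A Callaway–Sant'Anna group-time effect needs a baseline in the year before a cohort's start, and SDID needs a pre-period to weight on. A cohort already treated in the first data year has neither. A cohort first treated after the last data year has no outcome under treatment.

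The rent estimate would therefore describe a different set of places from the 1,635 LSOAs and five larger schemes that the plan reports. Newham, the second-largest London scheme by LSOA count, would not be in it. Controls matched only to the dropped schemes would stay in the comparison unless removed.

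The stated APS period raises the same question where it matters more: the APS carries the primary individual-level outcome and the life-satisfaction estimate behind the cost-benefit analysis.

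**Working it through.** **1. Reproduce the plan's totals.** The rows of Table S1, summed, give 61 schemes (32 + 14 + 15), 1,635 LSOAs, 1,356 LSOAs at 100% coverage and a population of 2,807,326. All agree with the table. The APS figure is 1,000 per year × 8 years (2012 to 2019) = 8,000, also as stated.

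**2. Count pre and post years by start year.** For start year *g* and data window *a* to *b*: pre years = *g* − *a*; post years = *b* − *g* + 1, with the start year as event time 0. A cohort needs at least one of each.

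| Start | Schemes | LSOAs | At 100% | Rent 2012–18 (pre/post) | APS as written 2012–19 | If 2011–19 |
|---|---|---|---|---|---|---|
| 2012 | 4 | 168 | 155 | **0**/7 | **0**/8 | 1/8 |
| 2013 | 3 | 10 | 3 | 1/6 | 1/7 | 2/7 |
| 2014 | 4 | 128 | 110 | 2/5 | 2/6 | 3/6 |
| 2015 | 12 | 757 | 730 | 3/4 | 3/5 | 4/5 |
| 2016 | 8 | 77 | 68 | 4/3 | 4/4 | 5/4 |
| 2017 | 8 | 72 | 58 | 5/2 | 5/3 | 6/3 |
| 2018 | 14 | 381 | 226 | 6/1 | 6/2 | 7/2 |
| 2019 | 8 | 42 | 6 | 7/**0** | 7/1 | 8/1 |

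The 2012 cohort is Blackpool 7 + Gateshead 4 + Wolverhampton 2 + Newham 155 = 168. The 2019 cohort is Blackpool 8 + Burnley 3 + Gateshead 1 + Middlesbrough 5 + Scarborough 3 + Wirral 4 + Great Yarmouth 4 + Slough 14 = 42.

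**3. Rent.**
- Schemes: 61 − 4 − 8 = 49.
- LSOAs at 5–100% coverage: 1,635 − 168 − 42 = 1,425, a loss of 210/1,635 = 12.8%.
- LSOAs at 100% coverage: 1,356 − 155 − 6 = 1,195.
- Larger schemes: 155 + 110 + 220 + 298 + 144 = 927; without Newham, 772 in four schemes.
- Control draws: matching is 1:3, so 210 × 3 = 630 of 1,635 × 3 = 4,905 draws belong to schemes that cannot contribute. Matching is with replacement, so the number of unique controls affected cannot be read from the documents.

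**4. APS.**
- Taken literally, 2012–2019 data leave 57 schemes and 1,635 − 168 = 1,467 LSOAs (1,356 − 155 = 1,201 at 100% coverage).
- With data from 2011, all 61 schemes have at least one pre year, and the 2012 cohort has exactly one.

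**5. Cohorts with three pre-intervention years.** The documents do not say whether the base year is one of the three, so both readings are shown.

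| First data year | Base year counted among the three | Separate base year needed |
|---|---|---|
| 2011 | 2014+ starts | 2015+ starts |
| 2012 (rent) | 2015+ starts: 757 + 77 + 72 + 381 = 1,287 of 1,425 LSOAs | 2016+ starts: 77 + 72 + 381 = 530 of 1,425 LSOAs |

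No reading covers the 2012 schemes.

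**The case against.** **On the APS.** The period 2012 to 2019 is also the window of scheme start years, and section 18 uses it that way. The statement that rent moves to 2012–2018 in place of 2011–2019, and the reason given for dropping the 2011 schemes, both imply that outcome data generally start in 2011. The 8,000 is a rough headcount, not an extraction specification. This stands. A reader might infer that no difference-in-differences exists for Newham on the primary individual-level outcome. The documents do not support that: they show an inconsistency about the first APS year, not an absence of 2011 data.

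**On the pre-trend test.** A reader might infer that the test covers 2015 and later starts only. That depends on a base-year convention the plan does not state, and with that convention it would be wrong for rent, where 2016 is the first eligible start. The plan also acknowledges that such tests may be underpowered and promises event-time plots alongside them.

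**On importance.** Rent is a secondary outcome. Leaving out cohorts that cannot be estimated narrows the estimand and does not by itself bias the estimate. The SAP also commits to justifying changes and publishing them, so it cannot be assumed that cohorts would vanish unreported. These points limit the consequence. They do not make the stated rent sample correct.

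**On mid-year starts.** Start months are not given, so part of 2012 may have been unlicensed in some schemes. With treatment coded by first calendar year, that does not create a pre year.

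**Conclusion.** For rent the plan is wrong as written. The 2012 schemes (168 LSOAs) have no pre-licensing year, contrary to the plan's own one-pre-year rule. The 2019 schemes (42 LSOAs) have no post year and can at most serve as not-yet-treated comparisons. The sample that can be estimated is 1,425 of 1,635 LSOAs, or 1,195 of 1,356 at 100% coverage. Both are given because section 18 names each coverage set as the main analysis in different places. This rests on annual coding by first treated year and on Table S1 listing each LSOA once, which its total of 1,635 supports.

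For the APS, the stated sample period conflicts with the one-pre-year rule and the implied 2011–2019 window. Whichever resolution is right, the text must change.

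The three-year pre-trend test gives no evidence on parallel trends for the 2012 schemes under any reading. Its coverage of the other early cohorts depends on the outcome and the base-year convention.

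The conclusion does not extend to SAMHI or the other area-level outcomes, for which a 2011 start is implied and nothing contradicts it.

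**What to change.** 1. **Rent.** Restrict treated schemes to 2013–2018 starts and state the resulting N. Remove controls matched only to the dropped schemes, recompute the matching weights and re-check balance by super-region. State whether 2019 LSOAs are used as not-yet-treated comparisons or left out. Report the larger-scheme subgroup as four schemes and 772 LSOAs, without Newham.
2. **APS.** Either state and extract 2011–2019 and restate the headcount (1,000 × 9 = 9,000, if the yearly figure also holds for 2011), or restrict APS analyses to 2013–2019 starts (1,467 LSOAs, or 1,201 at 100% coverage). Under the second option the headcount is about 7,100. That assumes respondents are spread in proportion to the Table S1 populations: the 2012 schemes hold 312,892/2,807,326 = 11.1%, and 8,000 × (1 − 0.111) ≈ 7,100.
3. **Pre-trend test.** State the base-year convention and, by outcome, the cohorts covered. Say that the test provides no evidence for the 2012 schemes.
4. **Table.** Add one short table giving the data window, eligible start years and number of treated LSOAs for each outcome.

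The cost is SAP wording, a re-run of the rent matching and balance tables and, if obtainable, one more APS year. The price is a smaller stated rent sample. The SAP is meant to be settled before any outcome analysis, so this is the cheapest time to make the change.

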#### Matching variables

We have chosen matching variables measured before the interventions or as close as possible to this time point from Census 2011, Indices of Multiple Deprivation, and council tax data. From Census 2011 we use the proportion of the population that are <16 years, proportion of the population aged 16 to 59 years, proportion of the population who are non-white and proportion of households from private rented sector. From the English Indices of Deprivation 2015, we use the proportion of population experiencing deprivation related to income, proportion of social and private homes that fail to meet the Decent Homes standard, proportion of households classed as overcrowded and an indicator of inability to afford to enter owner-occupation in the private rental market. Finally, we create a built pre-1945 indicator. The data on dwelling construction era were only 96.9% complete and were hence imputed sequentially with non-missing values from nearest LSOA11 neighbours (geodetic distance) (Table S3). For each LSOA11, the most common construction era was selected. In cases with ties (2.95%), the earliest construction era was selected.

#### 14b. Data sources

The APS data for the individual-level outcomes come from ONS and access to the data through the Secure Research Service (SRS) was approved on 2 Aug 2024 [47]. The sources of the area-level outcome measures are the University of Liverpool Place-based Longitudinal Data Resource [37], NHS Digital [48], Police.uk [49], University of Glasgow Urban Big Data Centre [46], and ONS [47]. The sources of LSOA characteristics used for matching are the Department for Levelling Up, Housing and Communities [50], and ONS [51,52].

# 15. Data collection and management

Qualitative data (forms and transcripts) will be collected by the LSHTM researcher ([name] and qualitative research fellow) and stored on LSHTM secure password-protected servers. [name] will be the data custodian for the qualitative data. Transcription will be carried out by a trusted, third party, EQ Transcription Services Ltd., [name], [contact] or an alternative transcription service recommended by LSHTM. The data will be anonymised and transferred using a secure file server. We will respect participants' right to withdraw from the study at any point. We will store data electronically, copying any paper-based data into an electronic format and destroying the paper originals securely. All data collected and produced by the project will be stored securely for 20 years.

Quantitative analyses will only involve secondary data and be carried out on password-protected university servers unless otherwise specified by agreements with data providers. Agreements with data providers will be adhered to – including use of secure data environments.

# 16. Blinding

Blinding is typically not feasible for natural experiments, e.g. if – as in this study - there are multiple control units per treated unit.

### 17. Potential bias

We will assess the robustness of our results in two ways: exposure falsification, i.e. assigning intervention status to a matched control area and outcome falsification, i.e. assessing an outcome

measure that is unlikely to be affected by SL. At area-level we will use annual precipitation as a placebo outcome. Each LSOA unit will be assigned the annual precipitation value (mm) of the nearest 12-km grid node. At individual-level we will explore the variables available in the APS for potential placebo outcomes.

# 18. Analysis plan

# Work package 1: Impact evaluation

### Objective

To assess area and individual level impacts of SL schemes on health and social outcomes. To assess impacts on equity.

### Selection of treatment areas

We have identified all Lower layer Super Output Areas 2011 (LSOA11) with 5 to 100% coverage of Selective Licencing (SL) schemes initiated between 2007 and 2021. These data were obtained through FOI requests to local authorities who provided information of the geographical areas covered by SL schemes. These could be based on various geographies (e.g wards, LSOAs, streets or other bespoke geographies). We mapped these geographies to LSOAs to provide the % of area in each LSOAs covered by a SL scheme. This process inevitably resulted in some small slivers and to avoid analysing areas that were potentially unexposed, LSOA11 with <5% area coverage were ignored.

We distinguish between treated areas, matched control areas, other untreated areas, and exclusion areas. The exclusion areas are defined as street-based schemes, pre-treated areas (2007-11), and future treated areas (2020-21). In addition, we define exclusive spillover areas as an alternative treatment category (see below).

Street-based schemes were taken out of the treated group and put in a separate category as there is insufficient contextual information on streets for the analysis, e.g. from official data sources such as Census (Table 3). We encountered three local authorities with street-based schemes, two solely street-based schemes in London and a small street-based scheme in a local authority that otherwise predominantly operated area-based schemes, Sheffield. In the case of the former, we have chosen to classify the whole local authority as 'Street-based schemes'.

LSOA11 treated before 2012 were removed from the treatment category and put in a separate category due to lack of outcome data for the early years of SL. Similarly, LSOA that were newly treated after the end of the 2012-19 study period, i.e. 2020-21, were put in a category of 'Future treated 2020-21' (Figure 1, Table 2).

We track how small areas (LSOA) have been part of one or more SL schemes over time within a local authority. The SL intervention will be analysed by the first year each LSOA11 was treated and treatment allocation has been fixed for methodological reasons regardless of whether a scheme got renewed after the first five years or not. Where the proportion of the LSOA covered by an SL scheme varied over time, the highest area proportion an LSOA11 unit had been exposed over time is used.

In the feasibility study in Greater London, partially treated areas were ignored. In the national study, however, many schemes could not be mapped 1:1 with LSOA11 units. They were either too small and/or defined with incongruent area units. Table S1 (Appendix I) shows the distribution of treated units by scheme and area coverage categories. The fragmented areas are likely to be different from the areas with larger and intact schemes such as London and Liverpool. It could hence create a selection bias problem if these more fragmented areas were excluded. Including the fragmented

LSOA11 units in the analysis (N=279), on the other hand, creates a measurement error problem (Figure S1). The main analytical approach will therefore be analysis of treated areas with 100% coverage accompanied by sensitivity analyses that gradually adds the more thinly covered areas until all areas with at least 5% coverage are included.

A total population of 2,807,326 (Census 2011) resided in the standardised LSOA11 areas across 64 SL schemes in 41 different local authorities (Table 2, Table S1). Within these schemes, 777,688 persons were living in private rental accommodation (Census 2011).

Table 2 Population estimates (Census 2011) and number of 2011 Lower Layer Super Output Area (LSOA11) units of Selective Licencing (SL) schemes in England 2012-19 by SL area coverage categories. The main analysis will be of the 5%-100% category as if fully treated. Sensitivity analyses will gradually deselect the more thinly covered areas until only fully treated areas are left, i.e. the '100% only' category.

| Coverage  | LSOA11 units | Population | Private rental tenants |
|-----------|--------------|------------|------------------------|
| 5%-100%   | 1,635        | 2,807,326  | 777,688                |
| 50%-100%  | 1,506        | 2,586,069  | 712,661                |
| 100% only | 1,356        | 2,329,792  | 637,541                |

[figure not shown]

Figure 1 Selective Licencing treatment, spillovers, and exclusion areas (2012-19) for London (left panel) and England (right panel with 5km buffer to highlight smaller schemes).

Table 3 Selective Licencing schemes in England 2012-19. Number of standardised 2011 Lower Layer Super Output Area (LSOA11) by region. Regions were defined as 1) The North (North East, North West, Yorkshire and The Humber), 2) The South (East Midlands, East of England, South East, South West, West Midlands), and 3) Greater London.

| Category               | The North | The South | London | Total  |
|------------------------|-----------|-----------|--------|--------|
| Untreated              | 7,561     | 17,465    | 1,916  | 26,926 |
| Treated                | 470       | 235       | 930    | 1,635  |
| Matched control        | 967       | 581       | 1,271  | 2,819  |
| Spillover single       | 293       | 233       | 271    | 797    |
| Spillover multiple     | 28        | 3         | 15     | 46     |
| Street-based schemes   | 2         | -         | 279    | 281    |
| Pre-treated 2007-11    | 94        | 7         | 9      | 110    |
| Future treated 2020-21 | 56        | 14        | 144    | 214    |

| Total | 9,471 | 18,538 | 4,835 | 32,844 |
|-------|-------|--------|-------|--------|

